Baseline characteristics will be reported, including age range and the proportions that are female, postmenopausal, and Caucasian. Means and standard deviations or medians and interquartile range will be reported for all continuous data, and non-continuous data will be reported as percentages. A log transformation may be utilized for any data that is not normally distributed. The three randomized study groups will be compared, based on the intent-to-treat principle, with respect to changes from baseline. Repeated measures analysis of variance will be used to compare groups using data from all time points together, though T-tests will also be used to compare pairs of groups with respect to differences between pairs of time points. Using actual administered doses, relationships between dose and changes over time will also be explored using appropriate linear or non-linear models to estimate dose-response relationships. Reports of blinded group summaries of adverse events will be regularly produced for safety monitoring.

b. Confidentiality

To maintain patient confidentiality, all study data will be de-identified. Each subject, upon enrolling in the study, will be assigned a three-digit subject number. Case report forms and the study database will identify each subject only by subject number and will contain no patient identifiers. De-identified case report forms will be kept within study binders, kept in a locked filing cabinet in a locked room. Completely de-identified study data will be stored in a data table maintained on a password-protected computer and stored on the Cleveland Clinic network, which is regularly backed up. The code identifying which patient belongs to each subject number will be kept in a separate locked filing cabinet in a locked room. Only the study coordinator and investigators will have access to this code.

REFERENCES

1. ATS statement: guidelines for the six-minute walk test. Am J Respir Crit Care Med 2002;166:111-7.

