2. **Quality of Life:** Measuring health-related quality of life is a key indicator of high-quality care. We will use two different, well-validated questionnaire to measure quality of life: The Kansas City Cardiomyopathy questionnaire and Camphor questionnaire. These are easy to complete and important to determining the effectiveness of therapy. [Questionnaires uploaded]

3. **Functional capacity & biomarkers:** Other traditional clinical parameters to assess therapy will be performed, including clinical status (WHO class), 6-minute walk, and aminoterminal B-type natriuretic peptide (NT-proBNP). All cause mortality and hospitalizations will be recorded for all participants in the study.

Study Design and Methods

A. Study Design

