If any patients in any arm of the study appear intolerant of drug (based on symptoms such as persistent light-headedness, sitting systolic BP<85 mm Hg or resting pulse<50, or hospitalization for heart failure), they will be provided a new bottle of pills labeled “week-dose reduction” as following: subjects on dose-escalating carvedilol will be provided a new bottle of carvedilol at the prior week's dose, subjects on fixed low-dose of carvedilol will be provided placebo pills, subjects on placebo will be provided a new placebo pill bottle. Once dose reduction has occurred in the dose-escalating arm, subjects will be maintained on that set dose throughout the remainder of the study, with no further escalation of dose. If signs or symptoms of subjects in any arm persist despite the dose reduction, dose reduction will again be implemented as follows: subjects on dose-escalating carvedilol will be provided a new bottle of carvedilol at half the current reduced dose, subjects on fixed low-dose carvedilol will again be provided placebo pills, subjects on placebo will again be provided a new placebo pill bottle. Of note, only 3 total dose reductions will be allowed during the entire 6 month study. Following 3 dose reductions are implemented, if subjects are still intolerant, they will be removed from all study drug.

Subject Instruction

All subjects will be advised to take the study medication with a small meal. All subjects will receive a daily phone call for the first week after start of carvedilol during the run-in. Thereafter, patients will be called weekly to screen for side effects and to monitor their clinical status. Patients will be provided a home blood pressure monitoring device and asked to record pulse and blood pressure in the morning and evening at the same time each day with instructions to call at any time systolic BP<85 mm Hg or pulse<55. Lightheadedness is expected to occur, but in 99.5% of cases in prior studies of severe heart failure, this resolves without problems. Patients will be instructed to sit up and rise slowly. Patients will also be instructed to call if they experience any new or worsening symptoms, or require hospitalization or unscheduled doctor visits.

F. Follow-up Schedule

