Subjects will be scheduled for follow-up visits at week 1, and months 1, 3, and 6. There is no scheduled follow-up of subjects after completion of the exit visit; subjects will then resume their standard of care clinical course. If patients were on carvedilol, the option to remain on therapy will be allowed based on patient and physician preference. If removal from therapy is requested by patient or physicians caring for the patient, carvedilol dose will be reduced by half every week until the patient is on 3.125 mg twice daily, at which time drug will be stopped.

At follow-up visits, subjects will bring their medications to check for compliance and correct dosage. At each visit, the subjects will undergo a physical exam including BP and pulse, pregnancy test, EKG, breathing tests, 6-minute walk, and echocardiogram, fill out questionnaires, and give a blood and urine sample. Please see Table A1 below for details.

At the study teams discretion and for patient's convenience study visits Screening Baseline and Run in may be combined.

G. Data Collection

Outcome data will be collected at the baseline visit and at follow-up visits at week 1, and months 1, 3 and 6. Safety monitoring parameters will be collected at all visits and via weekly phone calls throughout the study period.

Table 1. Procedures Performed at Each Visit

Procedure	Screening	Baseline	Run-in Week	Month 1	Months 3 & 6 (or upon study exit)
Chest X-ray	X*				
Blood draw for CBC, Complete metabolic panel, HIV, Hepatitis	X				
Blood draw for Erythropoietin		X			X
Cardiac-gated fasting FDG-PET		X			X (6 month only)
Blood draw for flow cytometry, plasma nitrite & nitrate, and GABR		X	X	X	X
Urinary nitrate		X	X	X	X
Exhaled NO		X	X	X	X
Saliva Collection		X			X (6 month only)
Quality of Life Questionnaires	X	X			X
Blood draw for NT-proBNP		X	X		X
Six Minute Walk Test	X		X		X
Echocardiogram		X	X		X
Electrocardiogram	X		X	X	X
Urine pregnancy test**	X	X	X	X	X

Spirometry & Diffusion capacity	X		X		X
Anticipated length of visit:	1 hour	5 hours	2 hours	2 hours	5 hours

*if not done in past year

**only women of child-bearing age

*** screening, baseline, run-in may be combined

Blood draws

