Safety monitoring parameters will be collected via daily and/or weekly phone calls and at all follow-up visits. Subjects will be asked whether they have experienced any side effects and to describe these symptoms and to provide the BP and heart rate home records, which will be recorded in the electronic medical record. We will also monitor subjects throughout their enrollment and record whether there have been any deaths or hospitalizations during the study.

Compliance

Subjects will be asked to bring the study medication and bottles with them to each follow-up visit. A tablet count will be performed to estimate compliance. Subjects will also be asked how many tablets per day they have been taking on average, and how many times a week they miss a dose.

H. Early Withdrawal

Patients may be withdrawn from the study for any of the following reasons:

- Pregnancy
- Lung transplantation
- Unacceptable side effects or toxicity, as deemed by the principal investigator
- Patient non-adherence or inability to communicate with the patient
- More than three dose reductions of medications required
- Patient request to withdraw from the study

I. Data Monitoring

a. Quality Control

Data will be monitored for quality control by the study coordinator, statistician and principal investigator. Within the study database, conventional limits will be set on each data entry cell to minimize entry of erroneous values.

b. Recruitment

Problems with recruitment will be assessed after 12 months of enrollment of the first patient. If less than a fourth of the sample size has been recruited for the study, additional recruitment strategies will be addressed and implemented.

c. Benefit/Risk and Subject Safety

This study will be submitted to the Institutional Review Board for review of the benefits and risks of the proposed trial. We plan to comprise a Data and Safety Monitoring committee to oversight

the trial. Overall, we believe the potential benefits of carvedilol for PAH outweigh the potential risks of the study.

Potential Benefits

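### Deaths and hospitalizations between early withdrawal and week 24 can go unrecorded, so the by-arm safety table may be incomplete, and biased if withdrawals differ by arm

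*Combined protocol and SAP*

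**What the plan says.** Specific Aims, B. Secondary Aim, item 3 lists death and hospitalization with the functional measures used to assess therapy: "All cause mortality and hospitalizations will be recorded for all participants in the study". It gives no observation period and no method of ascertainment.

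The method appears in section G, under Safety and tolerability outcomes: "We will also monitor subjects throughout their enrollment and record whether there have been any deaths or hospitalizations during the study".

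Section H (Early Withdrawal) opens with "Patients may be withdrawn from the study for any of the following reasons". The list includes "Unacceptable side effects or toxicity, as deemed by the principal investigator" and "More than three dose reductions of medications required", along with non-adherence, lung transplantation, pregnancy and patient request. The paragraph on carvedilol risks in section I also describes withdrawal from the study for unacceptable toxicity.

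Section F says: "There is no scheduled follow-up of subjects after completion of the exit visit". In Table 1 the last column is headed "Months 3 & 6 (or upon study exit"), so an exit visit can fall before month 6.

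Section E, Blinded Medication Dispensing, describes a similar patient differently: "Following 3 dose reductions are implemented, if subjects are still intolerant, they will be removed from all study drug". That sentence takes the patient off drug and does not mention leaving the study.

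The Analysis Plan compares the randomized groups by intent to treat on changes from baseline and produces blinded group summaries of adverse events. It names no between-arm test of deaths or hospitalizations.

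**The concern.** Death and hospitalization are the only hard clinical outcomes in this trial. The protocol's own background says that beta-blockade may have unfavorable consequences in this disease and that the balance of short-term risk and long-term benefit is untested. Readers will look at these counts by arm even without a formal test.

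Take a patient withdrawn at week 8 who dies or is admitted at week 14. The Secondary Aim suggests that this event should be known, but no procedure would find it. Several reasons for leaving relate to tolerability, so those who leave may be at higher risk than those who stay and may not be spread evenly over the arms. The intent-to-treat wording keeps patients in their assigned group after dose changes. It does not require data after withdrawal, and that is the gap.

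**Working it through.** **The plan's own figures.** Section C expects 30% loss in the run-in and 10% after randomization. 68 × 0.70 = 47.6, in line with the stated 48. 48 × 0.90 / 3 = 14.4 per arm, in line with the stated 14. The documents give no event rate, event count or power for deaths or hospitalizations, and the 10% is not split by arm.

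**Patients and follow-up affected.** 48 × 0.10 = 4.8, about 5 patients, or 1.6 per arm if allocation is equal at 16 per arm (assumed, since no ratio is stated). Follow-up per arm is 16 × 24 = 384 patient-weeks.
- Exit at week 4 loses 1.6 × 20 = 32 patient-weeks (8.3%).
- Exit at week 12 loses 1.6 × 12 = 19.2 patient-weeks (5.0%).

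**Direction and size of bias in the risk difference (carvedilol minus placebo).** Assumptions: exit at week 4, constant hazards, 24-week event risk r of 10% to 30% in patients who stay, and a hazard in leavers m = 1 to 3 times that of stayers. With λ = −ln(1 − r)/24, the chance that a leaver's first event falls after exit and before week 24 is

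q = exp(−4λm) − exp(−24λm).

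- r = 10%, m = 1: q = 0.983 − 0.900 = 0.083.
- r = 30%, m = 3: q = 0.837 − 0.343 = 0.494.

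With withdrawal proportions w_C (carvedilol) and w_P (placebo), bias = −(w_C − w_P) × q.

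| Withdrawal, carvedilol / placebo (assumed) | Bias, percentage points |
|---|---|
| 10% / 10% | 0.0 |
| 15% / 5% | −0.8 to −4.9 |
| 30% / 5% | −2.1 to −12.3 |
| 5% / 10% | +0.4 to +2.5 |

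Negative values favor carvedilol. Patients with missed events per 16-patient arm are 16 × w × q: 0.13 to 0.79 at w = 10%, and about 0.1 to 2.4 over all the proportions in the table.

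**Share of events missed, and the worst case for a ratio.** Assumptions: exit halfway on average, and an event rate after exit k = 1, 3 or 5 times that of other patients. If f is the share of follow-up time lost, the share of events missed is f·k / (1 − f + f·k).
- Leavers spread over all arms: f = 0.10 × 0.5 = 0.05. Missed: 5%, 14%, 21%.
- All leavers on carvedilol: f = (4.8/32) × 0.5 = 0.075. Missed: 7.5%, 20%, 29% on carvedilol and none on placebo. A true event ratio of 1.0 would read 1 minus those shares: 0.93, 0.80, 0.71.

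The second case uses raw counts over unequal follow-up. Per observed patient-time, the same inputs give 1 / (0.925 + 0.075k) = 1.00, 0.87, 0.77, so the distortion disappears at k = 1.

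**With the fix.** If every randomized patient is followed for events to week 24, missed events and this bias are zero by construction, apart from patients who refuse the contact.

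**The case against.** The case on the other side is substantial, and most of it limits the claim.

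- **A reader might infer two contradictory follow-up rules.** The documents do not clearly support that. The Secondary Aim speaks of participants in the study and section G of events during the study, and both can be read as the same window. The aim never mentions week 24.
- **A reader might infer that the plan says recording stops at early exit.** No sentence says so. The section F statement goes on to standard care and to continuing or tapering carvedilol, and can be read as applying at the end of the trial. It remains a fair inference that recording stops, because Table 1 allows an early exit visit and no text provides for later contact.
- **A reader might infer that the comparison leans toward carvedilol.** This is not shown. Dropout is not given by arm, withdrawal is judged blind, every randomized patient has tolerated the run-in dose, and several withdrawal reasons are unrelated to drug. Imbalance is still plausible. The run-in tests only 3.125 mg twice daily while the escalating arm may reach 25 mg twice daily, and the intolerance signs (low pressure, low pulse) are listed side effects of carvedilol. Blinding does not remove an imbalance that the drug itself causes.
- **Intolerant patients may stay in the study.** Section E takes them off drug only, and section H says they may be withdrawn, not that they must be. This also stands, and it is why the two passages need reconciling.
- **A hospitalization that leads to withdrawal occurs before exit and would be recorded.** True, but a later death or readmission would not be.
- **No event test is prespecified.** True. What is affected is a descriptive safety table. With so few events expected, one or two missed could change how that table reads.

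**Conclusion.** The concern holds as a gap in ascertainment. The plan names death and hospitalization as outcomes for all participants but contains no procedure for finding them between early withdrawal and week 24. At the planned 10% dropout this touches about 5 of 48 randomized patients. The safety tabulation is then incomplete. It is biased only if withdrawals differ by arm: toward carvedilol if toxicity withdrawals are more frequent there, toward placebo if the reverse, and roughly zero if they are equal.

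The size cannot be fixed from the documents. All bias figures rest on assumed event risks, exit times, hazard multiples and withdrawal proportions. The 0.71 to 0.93 ratios should be read as a worst case on raw counts with every leaver on carvedilol, not as an expected distortion. The case for a change rests on how little it costs to protect the only hard safety outcomes, not on a demonstrated bias.

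**What to change.** 1. In section G, Safety and tolerability outcomes, replace the sentence on deaths and hospitalizations with: *Vital status and all hospitalizations will be ascertained for every randomized patient through 24 weeks from randomization, by telephone or medical record, whether or not the patient remains on study drug or attends visits, unless consent for this contact is withdrawn.*
2. In section F, state that early exit ends study visits but not this event follow-up.
3. In the Analysis Plan, add a tabulation by randomized arm, over that fixed period, of deaths, hospitalizations and withdrawals with their reasons.
4. Reconcile section E (removal from study drug after three reductions) with section H (withdrawal from the study when more than three are required), so that it is clear who has left the study. Whichever way this is settled, the event follow-up in item 1 applies.

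Cost: a wording amendment, one added consent line, and calls or record checks for about 5 patients. The weekly calls and the electronic medical record are already in use. No dose or treatment rule changes.

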indicates no significant adverse effect on clinical functional status (NYHA class, walk distance, cardiac output, pulmonary artery pressure, pulse, blood pressure). Thus, we propose to determine whether treatment with a β -blocker reverses biochemical abnormalities in PAH that lead to maladaptive right ventricular remodeling and failure, utilizing a blinded, placebo-controlled, randomized trial of carvedilol in PAH patients for six months. We will also evaluate clinical parameters of cardiovascular function in relation to changes in the biochemical effects of treatment. Because PAH patients ultimately die of heart failure, carvedilol was chosen as the β -blocker in this study, as it is one of the two β blockers currently FDA-indicated for the treatment of heart failure, and has been extensively well-studied for use in very severe heart failure. Carvedilol blocks $\beta 1AR$ and $\beta 2AR$, as well as $\alpha 1AR$, the latter blocks vasoconstriction and may benefit for PAH patients by decreasing afterload. Additionally, carvedilol is inexpensive and generally well-tolerated; specifically, during long term treatment, intolerance to drug in patients with severe heart failure (class III-IV) did not differ from patients with mild-to-moderate heart failure (class II).

Specific Aims and Hypothesis

We hypothesize that use of carvedilol in patients with PAH will reverse loss of, and resensitize β -adrenoreceptors, increase production of NO, and reduce activation of HIF-1 α , which altogether will improve right and left ventricular function, decrease right and left ventricular size, and improve exercise and functional capacity. To test this, we propose a blinded, placebo-controlled, randomized trial of carvedilol at a fixed low-dose or dose-escalating pattern of therapy in PAH patients for six months with a one-week open-label run-in phase.

A. Primary Aim

To determine whether treatment with carvedilol reverses biochemical abnormalities associated with PAH, we will assess the following:

- Activation of HIF-1 α (co-primary end points):** We will assess activation of HIF-1 α via measurement of plasma erythropoietin and myocardial glucose uptake during fasting gated FDG-PET. We already know that erythropoietin is elevated in PAH and that FDG-uptake is high. We expect both to decrease on drug.

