Target enrollment for this study will be 68 patients. The primary outcomes FDG-PET uptake and erythropoietin, are anticipated to have positively skewed distributions, amenable to the use of ratios of 6-month measures relative to baseline to measure changes over time. Log transformed ratios are then anticipated to have approximately normal distributions. For secondary measures demonstrating less skewness or even approximate normality without the log transformation, absolute changes from baseline to 6 months will be used to measure change over time. Sample size is determined taking into account the power of the T-test for comparing the placebo and low dose carvedilol groups with respect to the reduction in FDG-PET uptake, as measured by the ratio of 6-month uptake to baseline uptake. Variability in FDG-uptake measures over 6 months suggests an expectation that the coefficient of variation in uptake ratios will not exceed 50%. Using a Bonferroni correction to adjust for multiple time points with $\alpha=0.025$, the T-test comparing log-ratios has 90% power to detect a difference in groups such that ratios have a 50% lower median for the low dose carvedilol group relative to the placebo group, if the groups contain $n=14$ subjects each. This effect size was selected based on previously observed reductions in FDG-PET uptake of roughly 50% among patients on β -blocker. Considering 10% potential dropout after randomization and a 30% potential dropout during the run-in phase, we intend to enroll 68 patients into the run-in phases, to achieve at least 48 patients eligible for randomization into the placebo, low dose Carvedilol, or dose escalation groups.

D. Enrollment

Recruitment Strategy

Patients who are diagnosed with PAH will be identified as potential subjects by either a nurse or doctor involved in the patient's disease management. These patients will be referred to the study investigators for screening and to obtain informed consent. Subjects will be recruited as they become available and without regard to gender, race, or ethnicity.

Informed Consent

All volunteers will be approached by the study investigators or their designee. The consent interview will take place the day of a patient visit to the Pulmonary Department. In a private examination room, one of the research investigators will explain the details of the study, to the

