Final eligibility will be determined by the investigator after review of the medical record and data gathered during the screening visit. Eligible, enrolled subjects will undergo additional baseline procedures:

- Quality of life questionnaires
- Fasting Gated FDG-PET scan
- Echocardiography
- Blood draw for flow cytometry, plasma nitrite and nitrate, global arginine bioavailability ratio (GABR), Erythropoietin, & NT-proBNP
- Urine for nitrate
- Exhaled NO

E. Intervention

Open-label Run-in Phase

All enrolled, eligible subjects will receive an open-label carvedilol therapy at starting dose of 3.125 mg twice daily for one week and be monitored at the Clinical Research Unit for the first-dose challenge of Carvedilol. Upon discharge, enough carvedilol to complete the 1-week run-in period will be dispensed by a licensed provider. Subjects will be instructed to return in 1 week with any

unused medication. Those individuals who are eligible for randomization to the trial will undergo the procedures summarized in Table A1 “Run-in Week”.

Double-blinded Randomized Phase

At the end of the 1-week run-in phase, subjects who have tolerated the low-dose carvedilol without severe or limiting side effects, still meet the inclusion and exclusion criteria, and who wish to continue in the study will be randomized to one of three arms: placebo, low-dose carvedilol, or escalating dose carvedilol for 6 months. Subjects and the investigators will be blinded to their group assignment for the duration of the study.

- Group 1 will receive a placebo drug to take twice daily for 6 months.
- Group 2 will receive carvedilol at a dose of 3.125 mg twice a day for 6 months.
- Group 3 will receive carvedilol in a dose escalation scheme. They will be given 3.125 mg tablets to take bid for 1 week, followed by 6.25 mg bid for 1 week, followed by 12.5 mg bid for 1 week with the option to increase to the max dose of 25 mg bid for the remainder of the study. During up titration, if a dose is not tolerated, the dose will be decreased to the previous tolerated dose for the remainder of the study.

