Doppler echocardiography will be performed by a single well-experienced echo technologist ([name]) for all studies to estimate PAP, RV and LV function using previously validated methods. Right ventricular function will be assessed via measurement of RV fractional area change (RVFAC), RV ejection fraction, myocardial performance index (MPI) of the RV, tricuspid annular plane systolic excursion (TAPSE), tissue Doppler-derived systolic velocity of the lateral tricuspid annulus (S' velocity), three-dimensional RV ejection fraction, and longitudinal strain and strain rate with tissue Doppler techniques (conventional technique, 2-dimensional speckle tracking and velocity vector imaging). Among these methods, the most used parameters are RVFAC, TAPSE, S' velocity of the lateral tricuspid annulus, and RV MPI.

Exhaled NO measurement

The participant will take in a deep breath and exhale through a mouthpiece attached to the nitric oxide analyzer (Aerocrine). This will be repeated for a total of three exhaled NO readings. NO is measured using the American Thoracic Society recommended guidelines.

FDG-PET scan

Cardiac-gated fasting FDG-PET scans will be conducted on fasting patients at baseline and 6 months. Finger stick blood sugar will be measured to assure fasting state (blood sugar < 120 mg/dl). Patient data will be acquired using a clinical PET/CT scanner (Biograph mCT 128) having time-of-flight capable PET detectors. First, a low-dose CT scan will be acquired to provide an attenuation map for PET data corrections. Then, a PET scan will be acquired in list mode for fifteen minutes with ECG signals obtained during the scan. Both static and gated images will be reconstructed using advanced iterative algorithms available on the scanner. All subjects will be fasting 8 h prior to and during the study, then injected with 370 MBq (10 mCi) FDG and scan performed at 1.5 h post-injection. Images will be analyzed in a blinded fashion by [name] using an image fusion workstation (MSViewer, CPS Innovations, Knoxville, TN) with region-of-interest (ROI) measuring tools. A total of five ROI will be measured in heart (left & right atria, RV, LV and IVS). In addition, ROI will be measured for the blood pool of the thoracic aorta. FDG uptake depends on factors including time between injection and scan, blood glucose, and body mass. For consistency, relative uptake will be normalized to blood pool FDG in thoracic aorta.

Safety and tolerability outcomes

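### The 0.025 significance level is justified by repeated time points that the FDG-PET test does not have, and no correction is stated for the two co-primary endpoints or the three arms

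*Combined protocol and SAP*

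**What the plan says.** - **Significance level.** Section C gives 0.025, with the reason "Using a Bonferroni correction to adjust for multiple time points with" that value.
- **Powered test.** Section C bases the size on "the power of the T-test for comparing the placebo and low dose carvedilol groups", applied to FDG-PET uptake at 6 months relative to baseline. It treats both primary outcomes as "amenable to the use of ratios of 6-month measures relative to baseline to measure changes over time".
- **Scan schedule.** The FDG-PET section says: "Cardiac-gated fasting FDG-PET scans will be conducted on fasting patients at baseline and 6 months". Table 1 agrees, with month 6 as the only post-baseline scan.
- **Erythropoietin schedule.** The Table 1 row "Blood draw for Erythropoietin" is marked at baseline and at months 3 and 6, so there are two post-baseline values.
- **Endpoints.** The Primary Aim labels HIF-1α activation "co-primary end points", assessed "via measurement of plasma erythropoietin and myocardial glucose uptake during fasting gated FDG-PET".
- **Arms.** Section E has subjects "randomized to one of three arms: placebo, low-dose carvedilol, or escalating dose carvedilol for 6 months".
- **Analysis.** The Analysis Plan (section G, Data Analysis/Reporting, part a) lists a repeated measures ANOVA over all time points and, in addition, T-tests between pairs of groups and pairs of time points. It states no adjustment.

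**The concern.** The reason given for 0.025 cannot apply to the test it is attached to, because a single 6-month ratio involves no repeated testing over time. The label may have been carried over from erythropoietin, where 0.05/2 would fit the two post-baseline draws. Read that way, the whole 0.05 goes to visits and nothing is left for the two endpoints or the arm contrasts.

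Three decisions are also unwritten: whether one or both co-primary endpoints must succeed, which arm contrast is primary, and whether the ANOVA or the T-tests decide. At stake is whether a positive primary result has a known false-positive rate. As written, the deciding endpoint, contrast and test could be chosen after unblinding.

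**Working it through.** **Inputs.** From section C: a 50% lower median ratio, coefficient of variation of the ratios at most 50%, level 0.025, 90% power, 14 per group, dropout of 10% after randomization and 30% in the run-in. Assumed, because the documents do not say: two-sided tests and an endpoint correlation of 0 to 0.8.

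**1. Reproducing the plan's figure.**
- Effect on the log scale: ln 2 = 0.693.
- Log-SD: √ln(1 + 0.5²) = √ln 1.25 = 0.472, or 0.5 if the coefficient of variation is read directly as the log-SD.
- Noncentrality: 0.693 / (SD × √(2/14)) = 3.88 at SD 0.472 and 3.67 at SD 0.5, with 26 df.
- Power at two-sided 0.025: **0.926** and **0.894**. The n needed for 90% power is 13 and 15, so the stated 14 lies between them.
- Dropout: 14/0.9 = 15.6, so 16 per arm and 16 × 3 = 48; 48/0.7 = 68.6, against 68 stated.

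The sample size follows from 0.025.

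**2. What 0.025 protects.** Simulation under the global null: three arms of 14, normal log-ratios, each t-test at two-sided 0.025, 200,000 replicates. A claim is allowed if either endpoint succeeds.

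| Tests allowed to support the primary claim | Error rate, endpoint correlation 0 to 0.8 |
|---|---|
| Low dose vs placebo, month 6, two endpoints | 5.0% to 4.0% |
| The same plus month-3 erythropoietin | 7.1% to 5.4% |
| Each carvedilol arm vs placebo, month 6, two endpoints | 9.3% to 7.4% |
| All three pairs, month 6, two endpoints (six tests), no gate | 12.7% to 10.2% |
| All three pairs, only after a three-arm F test at 0.025 per endpoint | 5.0% to 4.1% |

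The Bonferroni bound for the first row is 2 × 0.025 = 0.05. The second row assumes a correlation of 0.5 or 0.7 between the two erythropoietin visits. Its low end also depends on the correlation assumed between FDG-PET and month-3 erythropoietin.

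**3. Power under the possible rules (n = 14 per arm).**
- *Fixed sequence at 0.025 within each endpoint.* Error is at most 2 × 0.025 = 0.05. Power for FDG-PET, low dose vs placebo, stays 0.926 (0.894 at log-SD 0.5). If both doses have the same effect, power for escalating dose vs placebo, tested second, is 0.873 (0.824).
- *Three-arm F gate.* Power for low dose vs placebo is 0.867 to 0.926 (0.821 to 0.892 at log-SD 0.5). It is lowest when the escalating-dose effect is half the low-dose effect.
- *Both endpoints required, one named pair, each at 0.05.* Single-endpoint power at 0.05 is 0.962 (0.942). With independent endpoints, joint power is 0.962² = 0.926 (0.942² = 0.887). Over correlations 0 to 0.8 it is about 0.93–0.94 (0.89–0.91). The documents give no erythropoietin effect, so this assumes the same standardized effect as for FDG-PET.

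**The case against.** The strongest reply is that this is a mislabel and no more. 0.05/2 is exactly the split needed for two endpoints on one contrast, and section C fixes measure, time point, scale, test and level for that contrast. This stands: for low dose versus placebo at month 6, error is 4–5% and nothing but the label is wrong.

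A reader might infer more, namely that the trial's false-positive rate is 10–13%. The documents do not support that. No section makes all six tests confirmatory. Section C frames both primary outcomes as 6-month ratios, so month-3 erythropoietin is not named as a primary test. The Analysis Plan lists the ANOVA ahead of the pairwise tests; used as a gate at month 6, an overall test would hold error near 5%. The protocol also describes itself as a small mechanistic study. But no gate is written and no contrast is named primary, so the higher rates are not excluded either.

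Co-primary may also mean that both endpoints must succeed. The Primary Aim treats them as two measures of one construct and expects both to fall on drug. That is an expectation and not a decision rule. If it is the rule, no split over endpoints is needed. A reader might infer that it must cost power, but that follows only if 0.025 is kept on each endpoint.

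**Conclusion.** The concern holds as a fault in the stated reason for 0.025 and in what it covers. The time-point justification does not fit the test being sized, and the two endpoints and three arms have no stated correction. The sample size is sound: 14 per group gives roughly 90% power, and nothing here shows it to be too small.

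The size depends on what may support the primary claim. Error is about 4–5% for low dose versus placebo at month 6, 5–7% with month-3 erythropoietin added, 7–9% with both carvedilol arms versus placebo, and 10–13% with all six ungated tests. Every rate above 5% is conditional on tests that the documents neither declare confirmatory nor rule out. All the rates assume two-sided tests, normal log-ratios, an either-endpoint rule and an endpoint correlation of 0 to 0.8. The plan should be corrected before unblinding.

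**What to change.** In section C and in the Analysis Plan, replace the time-point reason with these statements:

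1. 0.025 is the Bonferroni split over the two co-primary endpoints, each tested at month 6.
2. Low dose versus placebo, the contrast the trial is sized on, is the primary contrast.
3. Month-3 erythropoietin is secondary.
4. Within each endpoint, the other arm contrasts are tested at 0.025 in a fixed, stated order, each only if the one before it succeeds.

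**Cost.** Only wording changes; 14 per group, 48 randomized, 68 enrolled and the stated power all remain. The escalating-dose contrast becomes confirmatory only if low dose versus placebo succeeds, with power of about 0.87 (0.82 at log-SD 0.5) if the two doses have the same effect.

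**Alternative gate.** An overall three-arm month-6 test before the pairwise tests gives both active arms equal standing. It can lower power for low dose versus placebo to about 0.87 (0.82 at log-SD 0.5), below the stated 90%. For FDG-PET with complete baseline and 6-month pairs, this gate is the ANOVA's group-by-time test on log uptake. For erythropoietin it would replace the all-time-points ANOVA as the deciding test.

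**If both endpoints must succeed.** Say so, limit the claim to low dose versus placebo at month 6, test each endpoint at 0.05 and report joint power. On the equal-effect assumption this is about 0.93–0.94 (0.89–0.91 at log-SD 0.5), essentially no loss against the stated 90%.
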